6.0 BACKGROUND DRUG INFORMATION

Ibrutinib

Ibrutinib is a small-molecule inhibitor of BTK. Ibrutinib forms a covalent bond with a cysteine residue in the BTK active site, leading to inhibition of BTK enzymatic activity. Ibrutinib 420 mg will be administered orally once daily. Ibrutinib should be administered at the same time each day with 8 ounces (approximately 240 mL) of water. The capsules should be swallowed intact and patients should not attempt to open capsules or dissolve them in water. If a dose of ibrutinib is not taken at the scheduled time, it can be taken as soon as possible on the same day with a return to the normal schedule the following day. Extra capsules of ibrutinib should not be taken to make up for the missed dose.

The first dose will be delivered in the clinic on Day 1, after which subsequent dosing is typically on an outpatient basis. Ibrutinib will be dispensed to subjects in bottles at each visit. Unused ibrutinib dispensed during previous visits must be returned to the site and drug accountability records updated at each visit. Returned capsules must not be redispensed to anyone.

Concomitant use of strong CYP3A inhibitors which would be taken chronically (e.g. ritonavir, indinavir, nelfinavir, saquinavir, boceprevir, telaprevir, nefazodone) is prohibited. Concomitant use of strong CYP3A inducers (e.g. rifampin, rifabutin, phenytoin, carbamazepine, and St. John's Wort) is prohibited. Avoid grapefruit and Seville oranges during ibrutinib treatment, as these contain moderate inhibitors of CYP3A.

6.1 How Supplied

Supplied as 140mg capsules. Ibrutinib will be supplied by Pharmacyclics LLC for a total of 2 years of therapy.

6.2 Stability

Store bottles at room temperature 20°C to 25°C.

6.3 Pharmacology

Ibrutinib was designed as a selective and covalent inhibitor of the Btk.(29) *In vitro*, ibrutinib is a potent inhibitor of Btk activity (IC50 = 0.39 nM). The irreversible binding of ibrutinib to cysteine-481 in the active site of Btk results in sustained inhibition of Btk catalytic activity

and enhanced selectivity over other kinases that do not contain a cysteine at this position. When added directly to human whole blood, ibrutinib inhibits signal transduction from the B-cell receptor and blocks primary B-cell activation (IC50 = 80 nM) as assayed by anti-IgM stimulation followed by CD69 expression.(30)

6.4 Pharmacokinetics and Product Metabolism

Following oral administration of ibrutinib at doses ranging of 420, 560, and 840 mg/day, exposure to ibrutinib increased as doses increased with substantial intersubject variability. The mean half life $(t_{1/2})$ of ibrutinib across 3 clinical studies ranged from 4 to 6 hours, with a median time to maximum plasma concentration (T_{max}) of 1 to 2 hours. Taking into account the approximate doubling in mean systemic exposure when dosed with food and the favorable safety profile, ibrutinib can be dosed with or without food. Ibrutinib is extensively metabolized primarily by CYP 3A4-mediated metabolic pathways. The on-target effects of metabolite PCI-45227 are not considered clinically relevant. Steady-state exposure of ibrutinib and PCI-45227 was less than 2-fold of first dose exposure. About 8% of ibrutinib is excreted renally. Ibrutinib exposure is not altered in patients with creatinine clearance (CrCl) >30 mL/min. Patients with severe renal impairment or patients on dialysis have not been studied. Following single dose administration, the AUC of ibrutinib increased 2.7-, 8.2and 9.8-fold in subjects with mild (Child-Pugh class A), moderate (Child-Pugh class B), and severe (Child-Pugh class C) hepatic impairment compared to subjects with normal liver function. A higher proportion of Grade 3 or higher adverse reactions were reported in patients with B-cell malignancies (CLL, MCL and WM) with mild hepatic impairment based on NCI organ dysfunction working group (NCI-ODWG) criteria for hepatic dysfunction compared to patients with normal hepatic function.

6.5 Summary of Clinical Safety

For more detailed information refer to the current version of the IB.

6.6 Precautions and warnings.

Bleeding-related events

There have been reports of hemorrhagic events in subjects treated with ibrutinib both with and without thrombocytopenia. These include minor hemorrhagic events such as contusion, epistaxis, and petechiae; and major hemorrhagic events, some fatal, including gastrointestinal bleeding, intracranial hemorrhage, and hematuria. In an *in vitro* platelet

function study, inhibitory effects of ibrutinib on collagen-induced platelet aggregation were observed. Use of ibrutinib in subjects requiring other anticoagulants or medications that inhibit platelet function may increase the risk of bleeding. A higher risk for major bleeding was observed with anticoagulant than with antiplatelet agents. Consider the risks and benefits of anticoagulant or antiplatelet therapy when co-administered with ibrutinib. Monitor for signs and symptoms of bleeding.

Supplements such as fish oil and vitamin E preparations should be avoided.

See Section 8.2.2 for guidance on concomitant use of anticoagulants, antiplatelet therapy and/or supplements. See Section 8.4 for guidance on ibrutinib management with surgeries or procedures.

Subjects with congenital bleeding diathesis have not been studied.

Leukostasis

There were isolated cases of leukostasis reported in subjects treated with ibrutinib. A high number of circulating lymphocytes (>400,000/µL) may confer increased risk. Consider temporarily withholding ibrutinib. Subjects should be closely monitored. Administer supportive care including hydration and/or cytoreduction as indicated.

Infections

Infections (including sepsis, bacterial, viral or fungal infections) were observed in patients treated with ibrutinib therapy. Some of these infections have been associated with hospitalization and death. Consider prophylaxis according to standard of care in subjects who are at increased risk for opportunistic infections. Although causality has not been established, cases of progressive multifocal leukoencephalopathy (PML) and hepatitis B reactivation have occurred in patients treated with ibrutinib. Subjects should be monitored for signs and symptoms (fever, chills, weakness, confusion, vomiting and jaundice) and appropriate therapy should be instituted as indicated.

Cytopenias

Treatment-emergent Grade 3 or 4 cytopenias (neutropenia, thrombocytopenia, and anemia) were reported in subjects treated with ibrutinib. Blood counts should be monitored monthly.

Interstitial Lung Disease (ILD)

Cases of interstitial lung disease (ILD) have been reported in patients treated with ibrutinib. Monitor patients for pulmonary symptoms indicative of ILD. Should symptoms develop, interrupt ibrutinib and manage ILD appropriately. If symptoms persist, consider the risks and benefits of ibrutinib treatment and follow the protocol dose modification guidelines (see Section 7.1)

Cardiac arrhythmias

Atrial fibrillation, atrial flutter and cases of ventricular tachyarrhythmia including some fatal events, have been reported in subjects treated with ibrutinib, particularly in subjects with cardiac risk factors, hypertension, acute infections, and a previous history of cardiac arrhythmia. Periodically monitor subjects clinically for cardiac arrhythmia. Subjects who develop arrhythmic symptoms (e.g., palpitations, lightheadedness, syncope or new onset of dyspnea should be evaluated clinically, and if indicated, have an ECG performed. For cardiac arrhythmias which persist, consider the risks and benefits of ibrutinib treatment and follow the protocol dose modification guidelines (see Section 7.1).

Tumor Lysis Syndrome

There have been reports of tumor lysis syndrome (TLS) events in subjects treated with ibrutinib therapy. Subjects at risk of tumor lysis syndrome are those with high tumor burden prior to treatment. Monitor subjects closely and take appropriate precautions.

Non-Melanoma Skin Cancer

Non-melanoma skin cancers have occurred in patients treated with ibrutinib. Monitor patients for the appearance of non-melanoma skin cancer.

Hypertension

Hypertension has occurred in subjects treated with ibrutinib. Regularly monitor blood pressure and initiate or adjust anti-hypertensive medication throughout treatment as appropriate.

6.7 Other safety observations.

Cerebrovascular Accidents

Although causality has not been established, cases of cerebrovascular accident, transient ischemic attach, and ischemic stroke including fatalities have been reported with the use of ibrutinib in the post-marketing setting, with and without concomitant atrial fibrillation and/or hypertension. Regular monitoring and appropriate treatment of conditions that can contribute to the occurrence of these events is recommended.

Diarrhea

Diarrhea is the most frequently reported non-hematologic AE with ibrutinib monotherapy and combination therapy. Other frequently reported gastrointestinal events include nausea, vomiting, and constipation. These events are rarely severe and are generally managed with supportive therapies including antidiarrheals and antiemetics. Subjects should be monitored carefully for gastrointestinal AEs and cautioned to maintain fluid intake to avoid dehydration. Medical evaluation should be made to rule out other etiologies such as *Clostridium difficile* or other infectious agents. Should symptoms be severe or prolonged follow the protocol dose modification guidelines (see Section 7.1).

Rash

Rash has been commonly reported in subjects treated with either single agent ibrutinib or in combination with chemotherapy. Rash occurred at a higher rate in the ibrutinib arm than in the ofatumumab arm in study 1112. Most rashes were mild to moderate in severity. Isolated cases of severe cutaneous adverse reactions (SCARs), including Stevens-Johnson Syndrome (SJS) have been reported in subjects treated with ibrutinib. Subjects receiving ibrutinib should be observed closely for rashes and treated symptomatically, including interruption of the suspected agent as appropriate. In addition, hypersensitivity-related events erythema, urticarial and angioedema have been reported.

Lymphocytosis

Upon initiation of single agent treatment with ibrutinib, a reversible increase in lymphocyte counts (i.e., ≥50% increase from baseline and an absolute count >5000/µL), often associated with reduction of lymphadenopathy, has been observed in most subjects (66%) with CLL/ small lymphocytic lymphoma (SLL) treated with ibrutinib as single agent. This effect has also been observed in some subjects with MCL (35%) treated with ibrutinib. This observed lymphocytosis is a pharmacodynamic effect and should not be considered progressive disease in the absence of other clinical findings. In both disease types,

lymphocytosis typically occurs during the first month of ibrutinib therapy and typically resolves within a median of 8.0 weeks in subjects with MCL and 14 weeks in subjects with CLL/SLL (range 0.1-104 weeks).

When ibrutinib was administered in combination with BR or with obinutuzumab in subjects with CLL/SLL, lymphocytosis was infrequent (7% with ibrutinib + BR versus 6% with placebo + BR and 7% with ibrutinib + obinutuzumab versus 1% with chlorambucil + obinutuzumab)

Lymphocytosis was not observed in subjects with Waldenström's macroglobulinemia treated with ibrutinib.

Overdose

There are limited data on the effect of ibrutinib overdose. No maximum tolerated dose (MTD) was reached in the Phase 1 study in which subjects received up to 12.5 mg/kg/day (1400 mg/day). Healthy subjects were exposed up to single dose of 1680 mg. One healthy subject experienced reversible Grade 4 hepatic enzyme increases (AST and ALT) after a dose of 1680 mg. Subjects who ingested more than the recommended dosage should be closely monitored and given appropriate supportive treatment.

Refer to Section 11.4 for further information regarding AE reporting.

7.0 DOSE DELAYS AND MODIFICATIONS

Section 7.1-7.3 outline recommendations for management of ibrutinib-associated toxicity. However, dose adjustments outside these guidelines can be made by the investigator if considered to be in the patient's best interests.

7.1 Recommended dose modifications:

Recommended dose modifications of ibrutinib are described below. For adverse reactions listed in Table 1, interrupt ibrutinib. Once the adverse reaction has improved to Grade 1 or baseline (recovery), follow the recommended dosage modifications.

Adverse Reaction	Occurrence	Dose Modification After Recovery Starting Dose = 420 mg
	First	Restart at 280 mg daily ^c
Grade 2 cardiac failure	Second	Restart at 140 mg daily ^c
	Third	Discontinue IMBRUVICA
Cuada 2 andia androthusia	First	Restart at 280 mg daily ^c
Grade 3 cardiac arrhythmias	Second	Discontinue IMBRUVICA
Grade 3 or 4 cardiac failure Grade 4 cardiac arrhythmias	First	Discontinue IMBRUVICA
Other Grade 3 or 4 non- hematological toxicities ^d	First	Restart at 280 mg daily
Grade 3 or 4 neutropenia with infection or fever	Second	Restart at 140 mg daily
Grade 4 hematological toxicities	Third	Discontinue IMBRUVICA

See Warnings and Precautions.

7.2 Hematologic toxicity:

Interrupt ibrutinib for any Grade 3 or greater neutropenia with infection or fever, or Grade 4 hematological toxicities. Once the toxicity has resolved to Grade ≤1 or baseline, reinitiate ibrutinib as per the table above.

7.3 Non-hematologic toxicity:

Interrupt treatment for any grade 3 or greater non-hematological toxicity. Once the toxicity has resolved to grade ≤1 or baseline, restart the study drugs as per the guidelines for the hematologic toxicity as above.

If the dose of ibrutinib is reduced, at the investigator's discretion, the dose of ibrutinib may be re-escalated after 2 cycles of a dose reduction in the absence of a recurrence of the toxicity that led to the reduction. Dose changes will be recorded in the medical record.

^b Grading based on National Cancer Institute-Common Terminology Criteria for Adverse Events (NCI-CTCAE) criteria, or International Workshop on Chronic Lymphocytic Leukemia (iwCLL) criteria for hematologic toxicities in CLL/SLL.

^c Evaluate the benefit-risk before resuming treatment.

^d For Grade 4 non-hematologic toxicities, evaluate the benefit-risk before resuming treatment.

These updated dosage modification recommendations may reduce the occurrence of additional serious events and are intended to improve tolerability for continued Imbruvica treatment.

7.4 Leukocytosis/Leukostasis:

A high number of circulating malignant cells (>400000/mcL) may confer increased risk of leukostasis; these subjects should be closely monitored. Administer supportive care such as hydration and/or leukophoresis as indicated. Ibrutinib may be temporarily held, and investigator should be contacted.

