7.5 Dose Modification for Hepatic Impaired Subjects

Subjects who develop acute hepatic toxicity with liver enzymes Grade 3 or higher while on study should be managed per standard dose modification guidelines in Section Error! Reference source not found. Ibrutinib is metabolized in the liver. In the population PK analysis (1,202 subjects), 179 subjects (14.9%) had mild hepatic impairment according to National Cancer Institute criteria and 12 subjects (1.0%) had moderate hepatic impairment. These subjects did not show a significantly higher ibrutinib exposure compared with subjects with normal hepatic function. In a hepatic impairment study, data showed an increase in ibrutinib exposure. For subjects with mild liver impairment (Child-Pugh class A), the recommended dose is 280mg daily. For subjects with moderate liver impairment (Child-Pugh class B), the recommended dose is 140mg daily. Monitor subjects for signs of ibrutinib toxicity and follow dose modification guidance as needed. It is not recommended to administer ibrutinib to subjects with severe hepatic impairment Subjects with clinically significant chronic hepatic impairment at the time of Screening (Child- Pugh class C) are excluded from study participation. Concomitant use of strong CYP inhibitors is not permitted in subjects with chronic hepatic impairment. Refer to Appendix D for Child-Pugh classification. Please refer to Table 3 for dose modifications due to hepatic impairment.

Table 1. Dose Modification Guidance for Hepatic Impaired Subjects

Child Pugh	class A	Child Pugh Cla	Child Pugh			
(Mild hepat	ic	(Moderate hepa	class C			
impairment)*	impairment)**	(Severe hepatic			
			impairment)			
Ongoing at	Develops	Ongoing at	Develops	Develops during		
time of	during	time of	during study	study		
enrollment	study	enrollment				

Ibrutinib	280 mg	280mg	140 mg	140 mg	Hold until
Dose					improves to
(daily)					moderate [Class
					B] or better)

^{*} If further reduction is needed due to non-hepatic toxicity, dose may be reduced to 140 mg. In the event that additional reduction is needed, ibrutinib should be held for non-hepatic toxicity until resolution.

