13.0 CRITERIA FOR REMOVAL FROM STUDY

Criteria for removal from study include, but are not restricted to, the following:

- Clinically significant progressive disease.
- Recurrent non-compliance by the patient with protocol requirements.
- Patient's request to be removed from the study.
- Occurrence of a CTCAE grade 4 non-hematologic adverse event, at least possibly related to ibrutinib. For CTCAE grade 4 adverse events that are numerically defined laboratory parameters, independent investigator assessment should be used to determine the risk:benefit for continuation of therapy.
- Occurrence of an adverse event which makes discontinuation from treatment necessary due to protocol specified safety criteria or desirable in the investigator's and/or the subject's opinion

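### Sections 7.1 and 7.3 give opposite instructions after certain cardiac events (discontinue versus restart), Section 13.0 adds a third rule for Grade 4 events, and nothing says which prevails

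*Combined protocol and SAP*

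**What the plan says.** Section 7.1 gives cardiac events their own rows. For the most severe, the row reads "Grade 3 or 4 cardiac failure Grade 4 cardiac arrhythmias First Discontinue IMBRUVICA", with no restart step. Grade 3 arrhythmia restarts at 280 mg after the first event and is discontinued at the second. The general ladder (280 mg, then 140 mg, then discontinue at the third event) applies to *Other* Grade 3 or 4 non-hematologic toxicities, where the entry begins "hematological toxicities ^d First Restart at 280 mg daily", and to the hematologic rows. Footnote d asks for a benefit-risk evaluation before treatment resumes after a Grade 4 non-hematologic toxicity.

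Section 7.2, on hematologic toxicity, says: "Once the toxicity has resolved to Grade ≤1 or baseline, reinitiate ibrutinib as per the table above".

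Section 7.3 says: "Interrupt treatment for any grade 3 or greater non-hematological toxicity". After resolution to Grade 1 or less or to baseline, the instruction is to "restart the study drugs as per the guidelines for the hematologic toxicity as above". No cardiac event is excepted.

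The opening of Section 7.0 calls 7.1 to 7.3 recommendations and adds that "dose adjustments outside these guidelines can be made by the investigator if considered to be in the patient's best interests".

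Section 13.0 lists among the criteria for removal: "Occurrence of a CTCAE grade 4 non-hematologic adverse event, at least possibly related to ibrutinib". Grade 4 events that are numerically defined laboratory values are left to a risk-benefit assessment instead.

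**The concern.** A clinician managing a first Grade 3 cardiac failure that has resolved finds *discontinue* in the table and *restart* in the paragraph written for non-hematologic toxicity. Both texts cover the event, and neither mentions the other's rule as an exception. Whether the patient is exposed to the drug again then depends on which paragraph is consulted.

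The stake is mainly patient safety. Inclusion criterion 3 in Section 4.1 requires that participants have no indication for CLL treatment, and Section 6.6 reports fatal events among the arrhythmias seen with ibrutinib. There is a secondary consequence for the trial's data: who stays on drug and under assessment may differ with the reading, and Section 11.0 counts a patient without a response assessment as a non-responder for the 24-month endpoint. The documents do not allow that second effect to be quantified.

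**Working it through.** No arithmetic applies, because the question is whether the instructions agree. The relevant events are set side by side below. The 7.3 column follows its reference to the hematologic guidelines, whose ladder is 280 mg, 140 mg, discontinue.

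| Event (after recovery) | 7.1 table | 7.3 read literally | 13.0 | Agreement |
|---|---|---|---|---|
| Grade 3 cardiac failure, first | Discontinue | Restart at 280 mg | No grade-based criterion | 7.1 and 7.3 opposed |
| Grade 3 arrhythmia, first | Restart at 280 mg, after benefit-risk evaluation | Restart at 280 mg | No grade-based criterion | Same dose step |
| Grade 3 arrhythmia, second | Discontinue | Restart at 140 mg | No grade-based criterion | 7.1 and 7.3 opposed |
| Grade 4 cardiac failure or arrhythmia, first | Discontinue | Restart at 280 mg | Removal, if possibly drug-related | 7.3 opposed to both others |
| Other Grade 4 non-hematologic toxicity, first | Restart at 280 mg, after benefit-risk evaluation | Restart at 280 mg | Removal, if possibly drug-related (laboratory values assessed individually) | 13.0 opposed to 7.1 and 7.3 |

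The next step is to look for any text that sets an order of precedence.

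1. *The chain from 7.3 to 7.2 to the table.* Section 7.3 refers to the hematologic guidelines, and 7.2 refers to the table. A reader who arrives at the table could apply the cardiac row. But 7.3 sends the reader there for the hematologic rule and has already ordered a restart, so the chain does not establish that the cardiac row governs.
2. *Section 6.6.* For arrhythmias that persist, it asks for a risk-benefit judgement and refers to Section 7.1. This favours the table for some arrhythmias. Section 6.6 has no entry for cardiac failure, so nothing similar exists there.
3. *Section 13.0.* Its grade-based criterion covers Grade 4 only. Its last item defers to safety criteria specified in the protocol, or to the opinion of the investigator or participant. For Grade 3 events that leads back to Section 7.
4. *The discretion clause in 7.0.* It permits departures from the guidance. It does not say which of two opposite statements is the guidance.

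None of the four settles the order. The clearest conflict is therefore the first row of the table. The second Grade 3 arrhythmia also conflicts, less sharply because of 6.6. The Grade 4 rows conflict through Section 13.0 as well as through 7.3.

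**The case against.** The best defence is that 7.3 has no ladder of its own. It borrows one, and in the 7.1 table that ladder is shared by the hematologic rows and the *Other* non-hematologic row. On that view 7.3 is only a prose version of the shared row, the cardiac rows are carved out by the word *Other*, and the specific entry overrides the general one. Section 6.6 supports this for persisting arrhythmias, Section 13.0 already addresses possibly related Grade 4 events, and all of 7.1 to 7.3 is guidance from which the investigator may depart.

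This is a reasonable reading and may be what was meant. It lessens the likely consequence, and it is why the point should not be described as a broken binding stopping rule. But the carve-out appears in the table and not in 7.3, which says *any* and *restart*, and no sentence supplies the precedence that the defence needs.

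A reader might also infer a wider conflict, which the documents do not support:

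- *Grade 2 cardiac failure.* Only 7.1 addresses it. Section 7.3 starts at Grade 3, so there is one instruction.
- *Re-escalation after two cycles at a reduced dose.* Only 7.3 addresses it, at the investigator's discretion and provided the toxicity has not recurred. Whether it extends to reductions made under the cardiac rows is unclear, but it contradicts nothing.
- *The hepatic-impairment footnotes in 7.5.* One says: "In the event that additional reduction is needed, ibrutinib should be held for non-hepatic toxicity until resolution". These footnotes concern further dose reduction in hepatically impaired patients. They are not about cardiac events, and a row that calls for discontinuation involves no reduction to trigger them.

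**Conclusion.** The concern holds in this form: 7.1 and 7.3 are opposed for a first Grade 3 cardiac failure and for a second Grade 3 arrhythmia. For Grade 4 non-hematologic events, 7.1, 7.3 and 13.0 do not give one consistent instruction. The text needs correcting as written, because following 7.3 literally re-exposes a patient whom 7.1 discontinues.

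The number of patients affected cannot be stated. A reader might apply the quoted atrial fibrillation rate of about 6% (Sections 3.5 and 3.8) to 50 patients, 0.06 × 50 = 3, and take that as the number facing opposite instructions. That does not follow. The figure is not limited to Grade 3 or above, and a first Grade 3 arrhythmia gets the same dose step under both sections. Only a Grade 4 or a second Grade 3 arrhythmia could meet the conflict, and the documents give no rate for either, or for cardiac failure. The 29% in Section 3.5 is all Grade 3 toxicity needing interruption and does not isolate cardiac events.

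The conclusion rests on two readings: that *discontinue* with no restart step means that treatment ends, and that *any* in 7.3 includes cardiac events. Both are the plain sense of the words. No view is taken on which clinical rule is right.

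**What to change.** Reconcile 7.1, 7.3 and 13.0 so that each event and grade has one instruction, and state which passage prevails if they differ. Two ways to do this are to have 7.3 refer to a single governing table in place of its own restart sentence, or to have 7.3 name the events that its restart sentence does not cover. For Grade 4 non-hematologic events, state how the removal criterion in 13.0 relates to the restart allowed by the *Other* row and footnote d. The same amendment should clarify whether the re-escalation text in 7.3 applies to reductions made for cardiac events. The sponsor, with the investigator, must decide which rule applies in each case.

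The cost is wording in one amendment, with the sponsor and IRB review that any amendment needs. It adds no visits, tests or patients and leaves the sample size and primary analysis unchanged.
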